Protocol Sobi.PEGCET-201 Page 35 of 39

13.2 APPENDIX II. DERIVATION RULES FOR TMA RESPONSE

[figure not shown]
eCRF forms: Platelet or PRBC Transfusion form, Central laboratory sampling form.

TMA response is defined as improvement in laboratory markers as follows:

IF [(LDH < 1.5 x ULN) AND (Platelet count ≥ 50*10^9/L (50 000/mm³)) AND ≥ 50% reduction from baseline in rUPCR AND

((Any blood transfusions performed=No) **OR**((Any blood transfusions performed=Yes) **AND** (Type of blood transfusion=PRBC **OR**Type of blood transfusion=Platelet) **AND** (Date of blood sample taken> Date of last platelet transfusion + 7 days)))]

THEN TMA response =1 **ELSE** TMA response=0

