Pegcetacoplan/TA TMA

Clinical Study No: Sobi.PEGCET-201

Blood and urine samples will be analyzed at a central laboratory unless a local laboratory facility is necessary, as defined in the laboratory manual. Urine samples will be analyzed by dipstick and microscopic analysis. All laboratory reports must be reviewed, signed, and dated by the investigator. A legible copy of all reports must be filed with both the patient's eCRF and medical record (source document) for that visit.

In the event that a patient's medical condition warrants rapid treatment initiation and the results of tests from the central laboratory cannot be awaited, results of tests performed at the site can be considered for screening purposes (inclusion/exclusion criteria checks), with the sponsor's agreement. In such cases, the local test results will be entered in the eCRF to confirm the eligibility.

Any laboratory test result considered by the investigator to be clinically significant should be considered an AE (clinically significant AEs include those that require an intervention), see Section 6.5.5.1.1 for details. Clinically significant abnormal values occurring during the study will be followed up until repeat test results return to normal, stabilize, or are no longer clinically significant.

The use of silica reagents in coagulation panels should be avoided. The sponsor previously conducted an investigation into prolonged aPTTs observed in subjects treated with pegcetacoplan. It was confirmed that false-positive aPTT prolongation occurred when coagulation panels were performed using a Stago Analyzer and, specifically, silica reagents. It was determined that there was interference between the silica reagents and PEGylated pegcetacoplan, resulting in artificially prolonged aPTTs.

If a patient has been tested for COVID-19, the results, if available, will be documented in the eCRF.

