### **MINIMUM STUDY REQUIREMENTS**

The following are the minimum study requirements for Study Sobi.PEGCET-201 during the COVID-19 pandemic and should be used as guidance when the full protocol requirements cannot be conducted.

1. **Obtain** key safety laboratory assessments.

Confidential Page 82 of 89

- Clinical Study No: Sobi.PEGCET-201
- a. All laboratory assessments should be drawn at the frequency required by the minimized schedule of events (Table 4).
  - i. Includes (at minimum): hematology with differential, chemistry including LDH and creatinine.
- b. In the event that the clinical investigative site is closed or patients are unable/unwilling to travel, patients should be referred to a certified local laboratory that can perform the required safety testing (see schedule of events below). The investigator should collect the local laboratory reports, which must be redacted (e.g., name and other local requirements) and added to the study records.
- 2. **Perform** minimal medical safety assessments.
  - a. If the patient is unable to have an in-person assessment, the investigator (or delegated site staff) should have a telephone contact at a frequency noted in the protocol (at minimum) to solicit AEs (including SAEs), concomitant medications and transfusions. The appropriate forms in the eCRF should be completed.
- 3. **Document** appropriate contact with the patient.
  - a. Earnest and reasonable attempts must be made to solicit AEs and concomitant medications. The CRA/medical monitor must be notified of any patients lost to follow-up.
  - b. All communication with the patient (including failed attempts at contact) must be documented in the study records.

The modified schedule of activities is shown in Table 4.

Confidential Page 83 of 89

Pegcetacoplan/TA\_TMA

Table 4 Revised COVID-19 minimum schedule of assessments

Study period	Screening		50		Treatn	Optional treatment		Follow-up period							
Study Week	-2	Baseline 0	1	2	3	4	6	8	10	12	14	16	EOT/ET ° 16	20°	EOS 24
Study Day	-14	1	8	15	22	29	43	57	71	85	99	113	113	141	169
Study visit	1	2	3	4	5	6	7	8	9	10	11	12	13	14	15
Visit window (± days)			(± 1)	(± 1)	(± 1)	(± 1)	(± 1)	(± 1)	(± 1)	(± 1)	(± 1)	(± 1)	(± 3)	(± 3)	(± 3)
Informed consent	X														
Demographics	X														
Medical history	X														
Inclusion/ Exclusion criteria	X	X													
Vaccination a	X														
Mandatory anti-infective prophylaxis b															

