5. SAMPLE SIZE AND POWER CALCULATION

This is a pilot study, and the sample size is based on practical rather than statistical aspects.

A total of 12 patients will be included and treated in the study. With 12 patients included, it is estimated that 9 patients will complete at least 4 weeks of treatment, which is deemed sufficient to characterize the PK of pegcetacoplan in patients with TA-TMA to an appropriate precision. In addition, 12 patients will provide a 72% probability to observe a response rate of at least 8 responders of the 12 patients recruited (assuming the true response rate is 70%).

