- Study days on or after the start day of study treatment will be calculated as the difference between the date of interest (TARGET DATE) and the first date of dosing of study treatment (TSTART) plus 1 day. The generalized calculation algorithm for the relative day is the following:
 - o If TARGET DATE ≥ TSTART then STUDY DAY = (TARGET DATE TSTART) + 1.
 - Else use STUDY DAY = TARGET DATE TSTART.

Note that Study Day 1 is the first day of study treatment. Study days on or before Day 1 are reflective of observations obtained during the baseline/Screening period.

Intervals that are presented in weeks will be transformed from days to weeks by using (with rounding

Page 18 of 39

to 4 decimal places) the following conversion formula:

• Intervals that are presented in months will be transformed from days to months by using (with rounding to 4 decimal places) the following conversion formula:

• Intervals that are presented in years will be transformed from days to years by using (with rounding to 4 decimal places) the following conversion formula:

All data collected will be presented in the data listings.

All the analyses will be descriptive, no hypothesis testing will be performed.

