8.8.2.9 DURATION OF TMA RESPONSE

Duration of TMA response (weeks) is defined as the time from the first observed TMA response until the response criteria is no longer fulfilled or until end of study. Duration of response will be defined for patients with TMA response without meeting ICE. The start date will be defined as the date of the earliest TMA response. Loss of TMA response as per appendix II (Section 13.2), reported TA-TMA relapse (from Survival Status eCRF form), and death from any cause will be considered events, with date of loss of TMA response, date of first reported TA-TMA relapse or date of death, whichever occurs first, defining the event date. Patients without events (i.e., still in TMA response) up to Week 24 will be censored at the date of the last TMA response prior to end of study.

The duration of TMA response (weeks) will be analyzed in the same way as Duration of Clinical Response (see Section §8.8.2.8 for details).

8.8.2.10 Proportion of Patients with TA-TMA relapse at week 24

Proportion of patients with TA-TMA relapse at week 24 will only be defined for patients reaching clinical response at some point of the study. TA-TMA relapse will be defined as reappearance of clinical/laboratory markers of TA-TMA as outlined in Inclusion Criterion #3. Counts and proportions of patients with and without relapse at Week 24 will be summarized. 95% Clopper-Pearson CI for proportion of patients with TA-TMA relapse will also be presented.

8.8.2.11 CLINICAL RESPONSE AT WEEK 12

Analysis of Clinical Response at Week 12 is covered in the Section §8.8.2.2.

8.8.2.12 TA-TMA RESPONSE AT WEEK 12

Analysis of TA-TMA Response at Week 12 is covered in the Section §8.8.2.3.

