13. APPENDICES

13.1 APPENDIX I. DERIVATION RULES FOR CLINICAL RESPONSE

eCRF forms: Platelet or PRBC Transfusion form, Central laboratory sampling form, Baseline TA-TMA form, Clinical Response Evaluation form,

```
Programming note: If central lab values not available, use local lab values reported on the clinical response evaluation form
Improvement in laboratory markers
IF [(LDH < 1.5 x ULN) AND (Platelet count ≥ 50*10^9/L (50 000/mm^3)) AND
               ((Any blood transfusions performed=No) OR
               ((Any blood transfusions performed=Yes) AND (Type of blood transfusion=PRBC OR
               Type of blood transfusion=Platelet) AND (Date of blood sample taken> Date of last platelet transfusion + 7 days)))]
THEN lab markers response =1 ELSE lab markers response=0
Renal response
IF (Has the patient any sign/symptom of kidney dysfunction=Yes) THEN DO
               IF [(((creatinine_baseline - creatinine)/creatinine_baseline) > 0.4)
               ((creatinine_baseline > ULN mg/dL (abnormal high)) AND (creatinine <= ULN mg/dL (normal))
               OR
               (discontinuation of renal replacement therapy=Yes)
               (((rUPCR_baseline - rUPCR)/ rUPCR_baseline) ≥ 0.5)]
               THEN renal response =1 ELSE renal response=0
END
ELSE renal response=0
Pulmonary response
IF (Has the patient any sign/symptom of lung dysfunction=Yes ) THEN DO
               IF [(Absence of positive pressure ventilation =Yes)
                (Absence of invasive ventilator support=Yes)]
               THEN pulmonary response =1 ELSE pulmonary response=0
END
ELSE Pulmonary response=0
Gastrointestinal (GI)
IF (Has the patient a biopsy-proven GI involvement of TA-TMA=Yes) THEN DO
               IF [(Presence of nausea, vomiting or anorexia attributed to TA-TMA=No)
               ((Stool output: in mL/day < 500 mL/day) OR (Stool output: number of episodes/day< 3 episodes/day))]
THEN GI response=1 ELSE GI response=0
ELSE Gastrointestinal response =0
Cardiovascular response
IF (Has the patient any sign/symptom of Cardiovascular dysfunction=Yes) THEN DO
               ((Has the patient a diagnosis of pulmonary hypertension = Yes) AND (Is pulmonary hypertension present=No))
               [((pre-antihypertensive therapy diastolic blood pressure ≥ 90 mmHg) OR
               (pre-antihypertensive therapy systolic blood pressure ≥ 140 mmHg) OR

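### Appendix II states no local-laboratory fallback for TMA response, although Appendix I has one for the same LDH and platelet criteria, so one visit can be classified differently in the two endpoints

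*SAP*

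**What the plan says.** Clinical response and TMA response share three conditions: LDH below 1.5 times ULN, platelets of at least 50 x 10^9/L, and no platelet transfusion in the preceding 7 days. TMA response adds a reduction of at least 50% in rUPCR.

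- **SAP 13.1 (Appendix I, clinical response)** includes the Clinical Response Evaluation form among its sources and carries a programming note: "If central lab values not available, use local lab values reported on the clinical response evaluation form".
- **SAP 13.2 (Appendix II, TMA response)** gives its sources as "eCRF forms: Platelet or PRBC Transfusion form, Central laboratory sampling form". It has no such note, and its ELSE branch assigns TMA response = 0.
- **SAP 8.8.2.7 and 8.8.2.9** both take TMA response from Appendix II. In 8.8.2.9 the events that end a duration include "Loss of TMA response as per appendix II (Section 13.2), reported TA-TMA relapse".
- **SAP 8.8.2.3** analyses TMA response in the same way as clinical response. The section it points to, 8.8.2.2, deals with counts, confidence intervals and intercurrent events, not with where a laboratory value comes from.

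The protocol foresees local results during the study. Section 6.5.5.2 has samples "analyzed at a central laboratory unless a local laboratory facility is necessary, as defined in the laboratory manual". Under the COVID-19 minimum requirements in Appendix 6, if the site is closed or the patient cannot travel, "patients should be referred to a certified local laboratory that can perform the required safety testing".

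**The concern.** Two endpoints that share criteria should read the same LDH and the same platelet count at the same visit. As written they may not. Where central values are missing and local ones are recorded, Appendix I uses the local values and Appendix II has no instruction to do so. TMA response could then depend on where a sample was processed, and the two endpoints would no longer be comparable at that visit.

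TMA response at Weeks 12 and 24, time to TMA response and duration of TMA response are exposed. The primary PK and safety endpoints and the sample size are not.

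Nothing suggests that the difference was intended. Protocol 6.5.7.2 does not restrict TMA response to central values, and SAP section 10 declares no such restriction as a departure from the protocol.

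**Working it through.** **Inputs.** From SAP section 5: n = 12, with "12 patients will provide a 72% probability to observe a response rate of at least 8 responders of the 12 patients", "assuming the true response rate is 70"%. SAP 8.1: "All the analyses will be descriptive, no hypothesis testing will be performed". The decision rules are those of Appendices I and II.

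**The plan's own figure.** P(X >= 8 | n = 12, p = 0.70) = sum over k = 8 to 12 of C(12,k) x 0.7^k x 0.3^(12-k) = 0.2311 + 0.2397 + 0.1678 + 0.0712 + 0.0138 = 0.7237 after rounding the unrounded sum, or 72.4%. This reproduces the stated 72%. The point below does not alter it; it supplies only the scale of n = 12.

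**One visit under both rules.** Assume for illustration a visit with no central LDH or platelet result, local LDH 1.2 x ULN, local platelets 80 x 10^9/L and no transfusion.

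| Rule | Values used | Shared LDH/platelet component |
|---|---|---|
| Appendix I | local | 1 |
| Appendix II as written | none available | 0 (ELSE branch) |
| Appendix II with the Appendix I note | local | 1 |

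TMA response at this visit still needs the rUPCR criterion, so restoring the shared component is necessary but not sufficient.

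**How the visit is then counted.** Two readings of Appendix II are possible.

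1. *Literal ELSE.* The visit is a non-response. One affected responder moves 8/12 = 66.7% (95% Clopper-Pearson 34.9% to 90.1%) to 7/12 = 58.3% (27.7% to 84.8%), a shift of 1/12 = 8.3 points. A first response would be dated to a later visit. A visit lying between two responses could count as loss of TMA response under 8.8.2.9.
2. *Missing.* SAP 8.3 leaves a visit without data missing, SAP 8.4 does not impute by default, and SAP 8.1 takes non-missing observations as the default denominator. Dropping one responder from 8/12 gives 7/11 = 63.6%, down 3.0 points. Dropping one non-responder gives 8/11 = 72.7%, up 6.1 points. For the sustained version of time to TMA response, 8.8.2.7 follows 8.8.2.6, under which a patient with a missing Week 24 evaluation is censored and is not a responder.

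**Frequency.** The documents give no rate of local-only visits. As an assumption, let a fraction q of true TMA responders have only local LDH or platelet values at Week 24, take a true rate of 70% (the sample-size assumption, which is not tied to a named response endpoint), and apply the ELSE reading. The expected observed rate is 0.70 x (1 - q):

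- q = 5%: 0.70 x 0.95 = 66.5%
- q = 10%: 0.70 x 0.90 = 63.0%
- q = 20%: 0.70 x 0.80 = 56.0%

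These figures show scale only; they do not predict what will happen.

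**The case against.** The strongest reply is that Appendix II omits local values but does not forbid them, and that the rest of the SAP softens the consequence. Several parts of this stand.

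- **Local values are not barred.** A reader might infer from Appendix II that they are. The text is only silent. The public copy also leaves out a figure just before the list of forms, so an unseen note cannot be excluded. Still, a programmer following the visible form list and ELSE branch would not use local values.
- **Loss of response is not certain.** A reader might infer that a local-only visit ends a TMA response. That requires the literal ELSE reading. SAP 8.3 and 8.4 point towards missing, and 8.8.2.6 separates a missing evaluation from a non-response. The SAP does not say which reading prevails.
- **A downward bias is not established.** A reader might infer a fixed loss of 8.3 points per affected patient. That holds only for responders under the ELSE reading; under the missing reading the rate can move either way.
- **Copying the note may not rescue a fully local visit.** The note reaches values recorded on the Clinical Response Evaluation form. Protocol 6.5.7.1 lists LDH, platelets and creatinine among the items collected at those evaluations, but not rUPCR. The minimum laboratory list in Appendix 6 does not name rUPCR either, although Table 4 keeps a row for it. Whether a local rUPCR is recorded cannot be determined from the documents.
- **Exposure may be small.** Central analysis is the default, Appendix 6 is temporary, and SAP 8.3 lets an unscheduled visit in the window replace a planned visit with missing data. A usable central sample in the window would remove the mismatch.

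None of this removes the basic difference: the two appendices apply identical LDH and platelet criteria with different stated sources, and no other passage reconciles them.

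**Conclusion.** The point holds as an inconsistency between the two derivation rules. At a visit with local but no central LDH or platelet values, the shared criteria can be met for clinical response while TMA response is 0 or missing. This rests on the visible text of Appendix II being complete and on such visits occurring, which the protocol allows and the Appendix I note anticipates.

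The effect is confined to secondary descriptive endpoints in a 12-patient pilot. One misclassified responder costs 8.3 points under the ELSE reading, against a 95% interval for 8/12 that is already about 55 points wide (90.1 - 34.9 = 55.2). Under the missing reading the illustrated shift is -3.0 or +6.1 points. The documents support neither a direction nor a frequency. The correction is worth making because it is cheap and because an unstated choice would otherwise be made during programming.

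**What to change.** State one laboratory-source rule for both appendices.

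1. Add the Clinical Response Evaluation form and the Appendix I programming note to Appendix II for LDH and platelets, and judge LDH against the ULN of the laboratory that ran the sample.
2. Name the source of rUPCR explicitly in both appendices, and use a local rUPCR only where one is recorded.
3. State that a visit with any required value unavailable from both sources is not evaluable: it is neither TMA response = 0 nor a loss of response under SAP 8.8.2.9. Patients with an intercurrent event remain failures as already specified.
4. Flag responses that rest on local values in the listing, and give the number of not-evaluable patients beside each Week 12 and Week 24 proportion, since the SAP 8.1 default removes them from the denominator.

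The cost is an SAP note and a small programming change. Using values already recorded needs no new data; where no local rUPCR was recorded, a fully local visit stays not evaluable. The downside is that central and local values are mixed in one endpoint, which Appendix I already accepts for clinical response.

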13.4 APPENDIX IV. TARGET MEDICAL EVENT

Table 2 - Definition of Target Medical Events

Target Medical Event	Search criteria in MedDRA	
Infections	SOC Infections and infestations	
Serious hypersensitivity reactions	SMQ Anaphylactic reaction (narrow) and SMQ Hypersensitivity (narrow)	
Infusion site reactions	HLT Injection site reactions and HLT Infusion site reactions

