### 4.3 Potential risks and benefits

Cumulatively, up to 13 May 2024, approximately 659 patients have been systematically exposed (via and s.c. route) to pegcetacoplan in completed and ongoing studies across multiple indications (refer to the pegcetacoplan IB). The administration of pegcetacoplan was well tolerated and the safety data did not indicate any significant safety concern. Nonetheless, a number of safety monitoring practices are being employed by this protocol to ensure patient safety, including physical examination, vital signs monitoring, ECGs, hematology (including coagulation), serum chemistry, urinalysis, and prompt reporting of AEs.

Confidential Page 27 of 89

Pegcetacoplan/TA\_TMA

Clinical Study No: Sobi.PEGCET-201

The event of hypersensitivity was identified as having a strong causal association with systemic pegcetacoplan. Cumulatively, in the systemic clinical development program for pegcetacoplan, 3 SAEs were assessed as related by investigators and the sponsor. Two SAEs of hypersensitivity and one SAE of hypersensitivity pneumonitis have been reported. The SAEs occurred in Study APL2-PNH-204 (hypersensitivity), Study APL2-ALS-206 (hypersensitivity), and Study APL2-302 (hypersensitivity pneumonitis).

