As with other complement-inhibiting drugs, there is a potential increased risk of infections with encapsulated pathogens including Streptococcus pneumoniae, Neisseria meningitidis (serogroups A, C, W, Y, and B), and Haemophilus influenzae Type B. Cumulatively in the systemic clinical development program for pegcetacoplan, 4 SAEs of infections associated with encapsulated bacteria have been reported. The 4 SAEs are comprised of 2 events of pneumococcal infection (1 pneumonia and 1 upper respiratory infection/epiglottitis), 1 event of pneumonia pneumococcal in Study APL2-C3G-310, and 1 event of Klebsiella pneumoniae in Study APL2-C3G-308. Three events of pneumococcal infections occurred in participants with renal disease; 2 of 3 were participants who had had a kidney transplant and were on immunosuppressive treatment. One case of Klebsiella pneumoniae occurred in a participant with PNH who had a history of medullary aplasia and pancytopenia. All cases were assessed as unrelated to pegcetacoplan by the sponsor. These cases were observed over 913.75 patient years of cumulative exposure in clinical studies (data until 13 May 2024, inclusive). The serious infections that were observed across studies were manageable. Therefore, the sponsor believes that the data do not support an increased risk of serious infections attributable to pegcetacoplan treatment.

However, as a precautionary measure, to reduce the risk of infection, patients taking pegcetacoplan should be vaccinated against *N. meningitidis* (Types A, C, W, Y, and B) either within 2 years prior to Day 1 or if clinically feasible, according to institutional guidelines for immune reconstitution after HSCT. Patients should be re-vaccinated against *H. influenzae* Type B and *S. pneumoniae* if clinically feasible, according to institutional guidelines for immune reconstitution after HSCT. All patients must continue to be administered coverage with prophylactic antibiotics and antifungals according to institutional posttransplant infection prophylaxis guidance, including coverage against *N. meningitidis*, for the entire treatment period and for 8 weeks following the final dose of pegcetacoplan.

Body temperature and vital signs will be monitored at all clinic visits and relevant blood parameters will be monitored throughout the study to assess for signs of infection. In the event of a suspected infection, the principal investigator should provide guidance on appropriate action to be taken.

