8.9.1 ADVERSE EVENTS

All AEs will be coded using MedDRA version current at the time of the DBL.

Pre-treatment AEs are those occurring between the ICF signature and the first IMP administration. TEAEs are defined as those AEs that start or worsen after the first dose of IMP and up to 8 weeks after the last IMP dose. Events will be flagged as treatment-emergent unless sufficient data are available to conclude that the start/worsening occurred before the treatment was started.

If the severity or relationship is missing for one of the treatment-emergent occurrences of an adverse event for a patient, the maximal severity or relationship on the remaining occurrences will be considered. If the severity is missing for all the occurrences, a "missing" category will be added in the summary table.

An overall summary table of the number and percentages of patients within the following categories will be provided:

- Any TEAE,
- Any related TEAE,
- Any serious TEAE,
- Any related serious TEAE,
- Any non-serious TEAE,
- Any related non-serious TEAE,
- Any TEAE leading to withdrawal of pegcetacoplan,
- Any serious TEAE leading to withdrawal of pegcetacoplan,
- Any TEAE leading to drug interruption,
- Any TEAE that is considered as a Target Medical Event as defined in Table 2 Definition of Target Medical Events,
- Any TEAE leading to death.
- Any TEAE that were infusion site reactions (as per eCRF, both injection and infusion site reactions

will be included).

- Any device related TEAEs (as per eCRF),
- Any TEAE by severity (mild, moderate and severe).

Pre-treatment AEs will be listed.

TEAEs, serious TEAEs, non-serious TEAEs, TEAEs by severity (mild, moderate, and severe), TEAEs related to pegcetacoplan, TEAEs leading to the withdrawal of pegcetacoplan, TEAEs leading to drug interruption, TEAEs that are considered as Target Medical Events, TEAEs that were infusion site reactions, device related TEAEs and AEs leading to death will be summarized by SOC and PT. Three categories of selected target TEAEs (Target Medical Events, defined in Table 2 - Definition of Target Medical Events) that are considered as Target medical Events will be summarized a posteriori. Summaries will include incidence of AEs, and number of events. The severity of AEs and the relationship to the IMP will be summarized for each SOC and PT.

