Pre-treatment AEs, TEAEs, serious TEAEs, non-serious TEAEs, TEAEs by severity (mild, moderate and severe), TEAEs related to pegcetacoplan, serious TEAEs related to pegcetacoplan, TEAEs leading to withdrawal of pegcetacoplan, and target medical events will be summarized by PT.

At each level of summarization, a patient is counted once if he/she reported 1 or more events at that level. These summaries by SOC and PT will be sorted by decreasing order of overall incidence of SOC and decreasing order of overall incidence of PT within SOCs. In case of identical frequencies, SOC and PT will be sorted alphabetically. The summaries by PT will be sorted by decreasing frequency of overall incidence of PT.

All AE data will be listed including onset date, duration, relationship to IMP, severity, seriousness, action taken with IMP, treatment of event and outcome.

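### The target medical event labelled as serious hypersensitivity is defined by MedDRA terms alone, so as written it would also count non-serious hypersensitivity TEAEs

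*SAP*

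**What the plan says.** SAP Appendix IV (13.4), Table 2, has two columns: the name of the target medical event, and its definition, headed "Search criteria in MedDRA". For the row named *Serious hypersensitivity reactions* the definition reads "SMQ Anaphylactic reaction (narrow) and SMQ Hypersensitivity (narrow" and contains nothing more.

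SAP 8.9.1 uses the table in two ways. The overview of TEAEs has a line for "Any TEAE that is considered as a Target Medical Event as defined in Table 2". Separate summaries are then planned for "Three categories of selected target TEAEs (Target Medical Events, defined in Table 2 - Definition of Target Medical Events"), by SOC and PT, and target events are also summarized by PT. SAP 10 notes that the analysis was added to what the protocol describes and gives no further rule for building the categories.

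The SAP treats seriousness as its own attribute. The same overview in 8.9.1 has lines such as "Any serious TEAE leading to withdrawal of pegcetacoplan", and the AE listing includes "relationship to IMP, severity, seriousness, action taken with IMP, treatment of event and outcome". Protocol 6.5.5.1.1 sets seriousness case by case, from the outcome or medical importance of the event.

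**The concern.** The label and the definition describe different sets of events. The label promises serious events; the definition returns every TEAE coded to a term in the two queries, whatever its outcome.

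The mismatch falls on a sensitive event. Protocol 4.3 states that "The event of hypersensitivity was identified as having a strong causal association with systemic pegcetacoplan", and it describes that experience by counting serious events: two of hypersensitivity and one of hypersensitivity pneumonitis. A reader of the study report would naturally set the row labelled serious beside those cases. If the row also holds non-serious events, the comparison is wrong, and in a safety set of 12 a single patient is enough to turn zero into a visible percentage.

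**Working it through.** The plan gives no figure for this category, so there is none to reproduce. The check is mainly one of definitions, followed by simple arithmetic on the size.

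**Step 1: is there a seriousness condition anywhere?**

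| Place | What it contributes | Seriousness condition for this row? |
|---|---|---|
| SAP 13.4, Table 2, label | The word serious | In name only |
| SAP 13.4, Table 2, definition | Two narrow SMQs | No |
| SAP 8.9.1, overview line | Any TEAE meeting Table 2 | No |
| SAP 8.9.1, summaries by SOC and PT, and by PT | The Table 2 categories | No |
| SAP 10 | Records that the analysis is new | No |

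**Step 2: could the search itself supply the condition?** No. A MedDRA search acts on the coded term. Under Protocol 6.5.5.1.1 two events with the same term can differ in seriousness, because seriousness depends on what happened to the patient.

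**Step 3: does the SAP usually state seriousness when it wants it?** Yes. In 8.9.1 the serious, non-serious and related-serious categories are each named as such. The target-event line refers to any TEAE.

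**Step 4: size per patient.** Input: 12 patients included and treated (SAP 5), all assumed to be in the safety set. Let k be the number of patients whose matching TEAEs are all non-serious. The row is raised by k/12:

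- k = 0: 0
- k = 1: 1/12 = 8.3 points
- k = 2: 2/12 = 16.7 points
- k = 3: 3/12 = 25.0 points

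**Step 5: how likely is k of at least 1?** The documents give no rate of non-serious hypersensitivity, so this can only be shown over an assumed range. If each patient independently has probability q of being such a case, the chance of at least one among 12 is 1 − (1 − q)^12 and the expected number is 12q:

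| Assumed q | Chance of at least one | Expected number |
|---|---|---|
| 5% | 1 − 0.95^12 = 46% | 0.6 |
| 10% | 1 − 0.90^12 = 72% | 1.2 |
| 20% | 1 − 0.80^12 = 93% | 2.4 |
| 30% | 1 − 0.70^12 = 99% | 3.6 |

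These values of q are illustrations, not estimates. The documents do not list the terms in the two SMQs either, so no particular kind of event can be named as one that would be caught.

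**The case against.** The best defence is that the label is the filter. The definition column holds MedDRA criteria, seriousness is not one, and so the label is the natural place to state it. A programmer could fairly apply label and search together. The mock tables, which might settle the matter, are a separate document (SAP 12). This part stands: the wrong count follows from the written rule but is not certain to appear in the output. It does not remove the point, because no text says that the label acts as a condition, and label and rule lead to two different tables.

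It is also fair that the true count can be recovered. Serious TEAEs are summarized by SOC and PT, related serious TEAEs by PT, and each AE is listed with its seriousness. With 12 patients the listing can be checked by hand.

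Three stronger readings are tempting, and the documents do not support them.

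- *A reader might infer that the primary safety analysis is misstated.* SAP 6.1 lists the primary safety endpoints, and target medical events are not among them. SAP 8.9.1 and 10 present them as a later addition. The stopping criteria in Protocol 6.1.5 do not use the row.
- *A reader might take the conjunction between the two SMQs to require a match on both.* The infusion-site row of Table 2 joins two searches in the same way, and for the separate eCRF-based infusion-site category 8.9.1 says that both types are included. In context the searches are pooled.
- *A reader might infer that defining infections by the whole SOC hides the concern in Protocol 4.3 that* "there is a potential increased risk of infections with encapsulated pathogens". Target events are also shown by PT, so an event coded to an organism-specific term has its own line, and the serious TEAE table by SOC and PT gives the serious infections. That row's label and definition agree.

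**Conclusion.** The point holds as a defect in one row of one table. As written, Table 2 and SAP 8.9.1 together would place non-serious hypersensitivity TEAEs under a serious heading. Each patient affected adds 8.3 percentage points, assuming that all 12 patients are in the safety set. How many patients would be affected cannot be derived from the documents, and no particular overstatement should be claimed.

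The consequence is confined to a supplementary, descriptive summary. No PK or efficacy result changes, and the tables of serious TEAEs and the AE listing are unaffected. It still deserves correction, because the row concerns the event most firmly tied to the drug and its label would be taken at face value.

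**What to change.** Before database lock, make one of two changes to SAP Table 2:

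1. Keep the label and add to the criterion that the AE must be flagged serious (AE serious = Yes).
2. Rename the row *Hypersensitivity reactions*, keep the two SMQs, and show the serious subset as a sub-row.

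Either makes label and rule agree. They are not identical in effect. The first removes non-serious hypersensitivity from the target events, and so can lower the overview line for any target medical event. The second leaves that line as the current rule would give it and shows both counts.

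The cost is one line in Table 2, one extra table row under the second option, and a matching edit to the mock tables if they differ. Seriousness is already recorded for each AE, so no new data are needed.
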